13.0 Risks to Participants

13.1 Foreseeable Risks: This proposed study involves human subjects. Human subjects are required for this study as we plan to test the effects of an intervention on human adults with thumb arthritis. This study cannot be carried out in an animal model nor does it pose any significant risks to the health and wellbeing of human subjects. 1) Participants might experience some mild hand fatigue or joint aches for 2-3 days following testing and at the onset of the intervention as a result of the repetitive nature of the tasks involved, 2) participants will be asked to give some information that you may be perceived to be of a personal nature 3) the primary outcome measure for this study is CT and this involves the aforementioned minimal amounts of ionizing radiation, and 4) at times, it may be necessary for the researchers to physically touch the participants' hands or sides to ensure that you are in the correct positions. This, to some, may be uncomfortable.

Radiation exposures will be minimized through short exposure times, and wear of leaded aprons, thyroid shields, and protective eyewear for the participant and rater alike, and leaded gloves for the rater.³⁹⁻⁴¹

Participants will be allowed frequent rest breaks to limit any amount of fatigue and soreness participants may experience in their hands and arms following testing and when participating in exercise. If discomfort increases as a result of testing, participants will be instructed on self-managing symptoms through use of physical agents such as cryotherapy and rest. In the event that this research activity results in an injury, treatment will be available, including first aid, emergency treatment and follow-up care as needed. Participants who believe they have suffered a research related injury, will be asked to inform the researchers immediately. If participants are physically uncomfortable or uncomfortable with the nature of the questions or occasional touch, they will be instructed that they are free to withdraw from participation at any time without any impact to relationships with the university.

Privacy/Confidentiality Risks: Risk of loss of confidentiality is unlikely, but could possibly occur as PHI is utilized as part of this study. This risk would be minimized by protections such as de-identification of participants via use of a study identifier, locked/secured/limited access to PHI, and electronic data securely stored and password-protected.

13.2 Reproduction Risks: Use of radiographic imaging is contraindicated for pregnant women. As such, women who are or could be pregnant will be excluded from this study.

13.3 Risks to Others: N/A

14.0 Potential Benefits to Participants

14.1 Potential Benefits: The occupational therapy services received by all participants is known to aid in pain reduction, can assist participants in developing health management strategies, and is known to reduce the experience of disability

15.0 Statistical Considerations

MEDICAL PROTOCOL (HRP-590)

PROTOCOL TITLE: Mechanisms of a Dynamic Stability Approach

VERSION DATE: 05/25/2023

15.1 Data Analysis Plan: For aim #1, the within-subjects outcomes will be compared primarily on the mean change in degree of subluxation from baseline to 9 week follow-up (the primary outcome). Additionally, given our recent retrospective findings²⁷ which support that advanced arthritic radiographic staging is also a negative predictor of response to the DS, mean change scores will be compared and adjusted for according to arthritic staging through use of linear regression for added precision of the treatment effect estimates. For aim #2, the agreement between baseline radial subluxation measurements via CT measurements and those via sonography will be assessed using the Bland-Altman method.⁴²

15.2 Power Analysis:

Aim #1: Previous work⁸ suggested that the mean immediate misalignment change in the treatment group will be 0.33 cm, with a standard deviation of 0.18. The proposed sample size was estimated a priori assuming a paired t-test of the change in misalignment, with two-tailed type I error of 0.05 and power of 90%. We conservatively estimate that the minimum clinically important change in misalignment will be between 0.05cm and 0.40cm, depending on how much the sustained effect is attenuated relative to the immediate effect (published value 0.42cm), and that the standard deviation (SD) of the misalignment measurement is 0.22cm. The correlation between the pre and post measurements is unknown, so we estimate the needed sample size for a range of correlation values between 0.20 and 0.80.

If we conservatively assume that the immediate misalignment change is 0.30cm, that the sustained change will be reduced by 50% to 0.15cm, and that the pre and post measurements will only be weakly correlated with a correlation coefficient of 0.2, then a sample size of 39 people (39 pre and post measurements) will be required. Assuming a potential loss-to-follow-up rate of 20%, we will enroll 49 participants.

Aim #2: A formal sample size estimate is not available for this aim given its novelty. However, because a sample of 30 participants is assumed to be adequate for bivariate correlational research³⁷, we anticipate that our sample of 49 participants will be adequately powered.

15.3 Statistical Analysis: See section 15.1.

15.4 Data Integrity: The PI is responsible for monitoring the integrity of the data. The PI will oversee regularly scheduled checks of both our outcome assessors and our interventionists. At each check, the PI will use a protocol checklist to document the number of evaluation and intervention protocol deviations and provide real-time feedback.

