Preliminary retrospective evidence suggests patients who participated in the DS program have better pain and disability outcomes than those who received standard care alone.^{9,10} However, major gaps in evidence for DS remain. Although evidence suggests that surgically stabilizing the thumb CMC improves hand function¹¹, the hypothesized sustained stabilizing effects of the DS exercise program have not been tested in prospective research. It is important to know whether a six week course of a DS program can reduce thumb instability and whether these benefits are possible for patients with a range of CMC OA severity. Additionally, because the gold standard of evaluating thumb instability is not within the scope of practice of rehabilitation scientists and therapists, they are limited in their abilities to visualize thumb CMC joint mechanics when treating and when evaluating response of treatment. Rehabilitation therapists and scientists can, however, be certified in musculoskeletal sonography and sonographic methods can be used to quantify thumb CMC alignment.¹² However, the agreement between sonographic and fluoroscopic or computerized tomography (gold standard) measures for assessing thumb CMC instability is unknown and must first be established.

The *long term goal* of my research is to help *mitigate the pain and disability experienced by persons with upper limb musculoskeletal disorders through non-invasive and non-pharmacological approaches*. The proposed research aims to prospectively evaluate the impact of DS exercises on the thumb instability in persons with thumb CMC osteoarthritis. My training plan supports this long-range goal by providing me the background needed to measure and/or interpret the outcomes of interest and carry out a single-arm intervention study.

We expect, in part, to achieve our long term and training plan objectives by pursuit of these **two specific aims:**

1. To describe changes in radiographic thumb CMC joint misalignment following a 6-week clinic-based dynamic stability exercise program. Fifty patients will be enrolled in a prospective pre-post interventional study of a 8-week clinic-based dynamic stability program and will undergo computerized tomography (CT) measurements before treatment, and upon completion of the program (9 weeks). The primary outcome will be change in CMC subluxation in cm from pre-treatment to post-treatment at 9 weeks.

MEDICAL PROTOCOL (HRP-590)

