2.3 Existing Literature: See section 2.1

3.0 Study Endpoints/Events/Outcomes

3.1 Primary Endpoint/Event/Outcome: CT assessments before treatment, and upon completion of the program (9 weeks). The primary outcome will be change in CMC subluxation in cm from pre-treatment to post-treatment at 6 and 12 weeks.

Secondary Endpoint(s)/Event(s)/Outcome(s): one-time assessment via use of musculoskeletal ultrasound during baseline and 9-week CT assessment session. Secondary analysis will also include records of treatment adherence and self-reported disability before treatment, and upon completion of the 8 week program (week 9).

[figure not shown]

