5.0 Procedures Involved

5.1 Study Design: aim #1 will be accomplished via a pre-post interventional design to evaluate changes in CT measurements of thumb radial subluxation (cm) from pre-intervention to intervention completion (9 weeks). The 9-week assessment will be the primary follow-up.

Aim #2 will be accomplished with a cross-sectional concurrent validity study design. Patients enrolled in the DS exercise intervention study will undergo additional assessment of metacarpal subluxation with ultrasound during baseline and week 9 evaluations.

5.2 Study Procedures:

Aim #1.

Screening and consenting: [name] has provided the CTSI's **BPIC** service with the diagnostic inclusion criteria for the study and will be informed within 3-5 days if a patient who meets these criteria is scheduled at the MHealth Clinics and Surgery Center. [name] will be present during the Study Orthopedist's clinic when these potentially eligible patients are scheduled for appointments. The study orthopedist will screen patients for pregnancy/risk of pregnancy via interview and present the study to the eligible patient and, if interested, the informed consent process will follow. [name] or other IRB-approved personnel will be responsible for informed consent. After consenting, baseline assessments will be conducted.

Assessment: CT will be used at prior to beginning aforementioned rehabilitation intervention, and after completing intervention (9 weeks) as per the European guidelines on quality criteria for computed tomography.³⁴ A validated positioning jig reproduced by our lab³⁵ will be used to maintain standardized joint positioning as the volunteer participates in dynamic pinch activities during CT examination. “Radial subluxation” (i.e., the displacement of thumb metacarpal base from the lateral border of the trapezium)³⁶ is a measure of thumb CMC instability and will be measured in centimeters. Subluxation measurements will not be made until after participants complete the 8-week protocol. After which, de-identified CT images will be presented to study orthopedic surgeon by the PI in a randomized sequence of baseline, and 9 week films so as to not introduce bias. Four images will be taken for each affected hand:

MEDICAL PROTOCOL (HRP-590)

PROTOCOL TITLE: Mechanisms of a Dynamic Stability Approach

VERSION DATE: 05/25/2023

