unloaded lateral pinch, loaded lateral pinch, unloaded 3-point pinch, and loaded 3-point pinch. When unilateral thumb OA is present, eight 3-second CT assessments (unloaded lateral pinch x2, loaded lateral pinch x 2, unloaded 3 point pinch x 2, and loaded 3-point pinch x2) will occur by the time of the 9 week follow-up. In the instance that the participant has bilateral CMC OA, 16 three-second assessments will occur. If participants have not yet had an x-ray confirmation of arthritis, through fluoroscopy will be billed to participant's insurance but CT assessments will all be billed to research.

Computerized tomography data will be recorded through use of the Siemens Biograph MCT 64 slice PET/CT at U of MN's Center for Clinical Imaging Research (CCIR). CT images will be used to capture 'kinematic' data and a wireless biometrics digital pinch meter will be used to capture the pinch 'kinetic' data.

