Home program	15-20 minutes Daily, 5 days a week	15-20 minutes Daily, 5 days a week	15-20 minutes Daily, 5 days a week	15-20 minutes Daily, 5 days a week	15-20 minutes Daily, 5 days a week	15-20 minutes Daily, 5 days a week	15-20 minutes Daily, 5 days a week	15-20 minutes Daily, 5 days a week
	Approximate duration of treatment per participant							840-1040 minutes

For **aim #2**, ultrasound measures will be obtained using a Sonosite X-Porte sonographic device. Sonographic assessment will occur at the time of participants'

MEDICAL PROTOCOL (HRP-590)

PROTOCOL TITLE: Mechanisms of a Dynamic Stability Approach

VERSION DATE: 05/25/2023

baseline and 9-week CT assessments (aim #1). The PI will conduct sonographic measures of radial subluxation on all Aim #1 participants (n=49). The same stress view, positioning jig and standardized upper limb postures used for Aim #1 will again be employed. In addition to these standardized joint postures and forces, the thumb CMC joint sonographic procedures described by Oo et al.¹² and the general guidelines put forth by American Institute of Ultrasound in Medicine³⁷ will be followed. The device is the property of [name] and there will be no charges billed to the participant associated with the use of this instrument. [name] will work with [name] from Fairview's biomedical engineering dept. to ensure the device is approved for use at the MHealth Clinics and Surgery Center.

The PI will quantify radial subluxation (cm) of the thumb metacarpal in the same manner as it was in Aim #1. The agreement between these values and those gathered through CT in Aim #1 will subsequently be assessed. The PI and the orthopedic surgeon evaluator will be blinded to each other's ultrasonography and CT findings.

The intervention and baseline diagnostic fluoroscopic assessment are standard care and would be conducted even if not for the purposes of this study. Sonography and the CT measurements would be considered above and beyond standard care.

Data to be pulled from patient records include age, sex at birth, arthritis staging, concomitant health conditions, pain, thumb mobility measurements, and disability ratings. Secondary data on treatment adherence via an exercise log and self-reported disability will also be captured (Michigan Hand Questionnaire) for secondary analyses.

Lastly, participants will be asked to report on adverse events during each encounter during weeks 1-6.

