Assessment	Screening , Baseline: Visit 1 (Day 0, Week1)	Treatment Visit 1 (Week 1)	Treatment Visit 2 (Week 3)	Treatment Visit 3(Week 5)	Treatment Visit 4 (Week 7)	Follow-up #1 (Week 9)
Informed Consent Form	X					
Demographics	X					
Medical History/Arthritic staging	X					
Inclusion/Exclusion Criteria (Including radiographic confirmation of OA via fluoroscopy)	X					
Attestation of certainty of not being pregnant by women who are non-post menopausal	X					
Enrollment	X					
CT Measurements (Aim 1)	X					X

MEDICAL PROTOCOL (HRP-590)

PROTOCOL TITLE: Mechanisms of a Dynamic Stability Approach

VERSION DATE: 05/25/2023

Ultrasound measurements (Aim 2)	x					x
Self-reported disability (Michigan Hand Questionnaire) – Aim 1b	x					x
Treatment Adherence (Exercise Log) – Aim 1b		x	x	x	x	x
Adverse Events		x	x	x	x	x

Note: "Week" = 7 days +/-3 days

5.3 Study Duration:

- Duration anticipated for an individual participant's participation in the study: 9 weeks
- The duration anticipated to enroll all study participants: 3 years
- The duration anticipated to complete all study procedures: 4 years

5.4 Use of radiation:

Note: the following calculations are based on static radiographic imagining.

Radiation exposures (Aim#1) will be minimized through, short exposure times, and wear of leaded aprons, thyroid shields, and protective eyewear for the participant.

Leaded aprons, thyroid shields, and leaded eye protection will worn by the evaluators and participants throughout each CT assessment. Without the attenuation expected from the above protective measures, a conservative estimate of maximal radiation exposure per session is 0.0078 mSv (totaling 0.1248 mSv) when both thumbs are measured and 0.0624 mSv when only measuring one.

This exposure would respectively equate to 2.3% (unilateral) or 4.6% (bilateral) of the radiation one is naturally exposed to each year as a resident of Minnesota (3 mSv).⁴² Additionally, because investigators will not be working near but not within the beam of the CT device so there is no risk to the investigators.

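### Does taking four CT images per affected hand undermine a sample size that counts one pre/post pair per person?

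*Combined protocol and SAP*

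**What the plan says.** Section 1.1 (specific aim 1) defines the outcome without naming an image or a hand: "The primary outcome will be change in CMC subluxation in cm from pre-treatment to post-treatment at 9 weeks". Section 3.1 is equally general: "The primary outcome will be change in CMC subluxation in cm from pre-treatment to post-treatment at 6 and 12 weeks". The different follow-up weeks in those two sentences are a separate matter.

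Section 5.2 gives the acquisition plan: "Four images will be taken for each affected hand". The four are lateral pinch and 3-point pinch, each with and without load, at baseline and at week 9. For two affected thumbs, "In the instance that the participant has bilateral CMC OA, 16 three-second assessments will occur". Section 5.4 gives dose totals on the same basis: "a conservative estimate of maximal radiation exposure per session is 0.0078 mSv (totaling 0.1248 mSv) when both thumbs are measured".

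Section 15.2 states the unit used for sample size: "then a sample size of 39 people (39 pre and post measurements) will be required". Section 15.1 analyses the mean change and adjusts it for arthritis stage by linear regression. Section 11.1 closes a stage stratum once it holds 16-17 participants. For Aim 2, section 5.2 says of the ultrasound measurement: "The same stress view, positioning jig and standardized upper limb postures used for Aim #1 will again be employed".

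**The concern.** The sample size rests on one pair per person, while the imaging schedule yields four or eight. A reader looks for the rule that reduces these to one number and does not find it. The text names no image, no average or contrast, no index hand for bilateral disease, and no thumb whose stage sets the stratum and the covariate. Aim 2 adds to the doubt by mentioning a stress view, although the Aim 1 list contains only pinch images.

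This is the primary outcome of a single-arm study. Two analysts could compute different primary estimates from the same films. If the choice were made after looking at results, a chance change would be declared real more often than 5% of the time. A bilateral participant whose thumbs are at different stages could be counted in either of two strata.

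**Working it through.** **1. Reproduce the plan's figure.** Inputs from 15.2: change 0.15 cm, SD of one measurement 0.22 cm, pre/post correlation 0.2, paired t-test, two-sided 0.05, power 90%, loss 20%.

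- SD of change = 0.22 × √(2 × (1 − 0.2)) = 0.278 cm.
- Noncentral-t power is 0.899 at n = 38 and 0.907 at n = 39, so 39 are needed.
- 39 / 0.8 = 48.75, so 49 are enrolled. Both stated numbers reproduce.

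**2. Count the images.** One affected thumb: 4 images × 2 visits = 8, or 4 pairs. Two thumbs: 16, or 8 pairs. For 39 people that is 39 × 4 = 156 to 39 × 8 = 312 pairs. The dose totals agree: 0.0624 / 0.0078 = 8 and 0.1248 / 0.0078 = 16. This is weak support, because 5.4 calls 0.0078 a per-session figure.

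**3. Do the counts conflict?** No. Section 5.2 counts acquisitions and 15.2 counts analysed pairs. Any rule that gives one value per person per visit yields 39 pairs from 39 people. Section 15.2 also rules out the naive alternative: treating 156 images as independent would give a type I error of about 0.16, 0.22 or 0.30 at between-image correlations of 0.3, 0.5 or 0.8.

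**4. What sensible choices do to the sample size**, if 15.2's inputs hold for each image:

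- One named image on one hand: 39.
- Mean of the four images on one hand: SD = 0.278 × √((1 + 3r)/4). The need is 20, 25, 31, 36 or 39 at an assumed correlation of change r of 0.3, 0.5, 0.7, 0.9 or 1.0.

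Neither exceeds 39.

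**5. How far apart the images' estimates could be.** Suppose the true change is the same in all four. The expected range of four mean changes is 2.058 × SE × √(1 − r), with SE = SD of change / √39. The documents do not give r; 0.5 to 0.8 is assumed.

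| Pre/post correlation (15.2) | SE (cm) | Range at r = 0.5 | Range at r = 0.8 |
|---|---|---|---|
| 0.2 | 0.0446 | 0.065 cm | 0.041 cm |
| 0.8 | 0.0223 | 0.032 cm | 0.021 cm |

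These compare the largest with the smallest. Two analysts who happen to pick different images differ on average by (2/√π) × SE × √(1 − r). At r = 0.665 this is 0.029 cm (19% of 0.15 cm) for pre/post correlation 0.2, and 0.015 cm for 0.8.

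The value 0.665 is 1 − 0.18² / (2 × 0.22²). It takes 0.18 as the SD of change, since 0.33 / (0.18/√32) = 10.4, close to the t of 10.6 in 2.2. It comes from maximal contraction in 32 non-arthritic hands and is a correlation of levels, so it is only a rough guide to changes under pinch in arthritic thumbs.

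**6. If the image were chosen for its CT result.** With no true change, at least one of four tests has p < 0.05 in 15.9%, 13.6% or 11.4% of simulated studies at r = 0.5, 0.665 or 0.8.

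**7. The stress view.** Section 5.2 takes its positioning jig from a cited stress-view evaluation system and its subluxation measure from a cited study of the stress-view radiograph. The Aim 2 wording can be read as that set-up, with the pinch images taken in it.

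**The case for a change.** The strongest case for a change concerns who could make the choice and when. De-identified CT films read in random order protect each reading, but not the later selection of an image or hand. The PI measures ultrasound subluxation in the same postures at both visits and, under 18.2, is responsible for the analysis. The PI could therefore know which condition moved before the CT films are read. Picking the condition with the largest ultrasound change would give a false-positive rate of 10.0% if ultrasound and CT changes correlate 0.7 (7.6% at 0.5, 12.4% at 0.9). In bilateral disease, picking the more subluxated thumb at baseline would create a spurious reduction of 0.054 to 0.083 cm per bilateral participant at pre/post correlation 0.2 (0.014 to 0.021 cm at 0.8), for an assumed between-hand correlation of 0.3 to 0.7. A single-arm design has no control group to cancel this. Writing the definition down would take a few sentences.

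What stands is that the definition is absent and that choosing by results would be harmful. What does not stand is that the plan calls for such a choice. Nothing in it selects a condition by ultrasound or a thumb by severity. The ultrasound-CT correlation is assumed, and 1.1 itself says the agreement between ultrasound and the reference methods is unknown. The documents do not give the share of bilateral participants, or of those with thumbs at different stages.

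**Conclusion.** No change to the plan follows. This is missing detail that a competent analyst fills in: one value per person per visit, set before the CT readings are opened, with the stage taken from the thumb that is analysed. Section 15.2 points to that unit, a paired t-test on it is valid, and 39 evaluable and 49 enrolled are correct for it. Stage enters only to balance recruitment and to adjust the estimate, so a participant with discordant thumbs raises a bookkeeping question, with no effect on the validity of the primary comparison.

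The remaining exposure is modest. Equally reasonable images would give mean changes that span about 0.021 to 0.065 cm on average, against a planned 0.15 cm, under the correlations assumed above and equal true change in all four. The inflated error rates are conditional on a result-driven choice that the plan does not describe. Aim 1 is also framed as describing change, and 15.1 states no test.

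The conclusion assumes that 15.2's change, SD and correlation apply to the value analysed. At SD of change 0.278 cm, a true change of 0.10 cm would need 84 people and one of 0.20 cm would need 23. That sensitivity belongs to any such calculation, and 15.2 already acknowledges a range of effects and correlations.
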